7.2. Dosing strategy

A sentinel dosing strategy will be used in both Part A (SAD) and Part B (MAD), except for the food and gender effect cohorts. The investigator and the Sponsor will assess safety and tolerability data and determine whether it is acceptable to continue dosing (within cohorts) or to dose escalate (between cohorts).

[Table 5](#) summarizes the sentinel dosing strategy as the following. The first 2 subjects (1 on SKL24741 and 1 on placebo) within each cohort may be dosed at the same time. Randomization will ensure that one of these 2 subjects (sentinel subjects) receives placebo. If the doses are safe and tolerated, as determined by the investigator and the Sponsor, dosing of the remaining subjects will occur after the observation period as specified in [Table 5](#).

Table 5: Sentinel Dosing Strategy

Dose level (Part A and Part B)	Observation Period and Safety Review
First dose level	1) Two sentinel subjects (1 on SKL24741 and 1 on placebo) 2) 14-day observation period after dosing the first subject with SKL24741 3) The investigator and the Sponsor review all available blinded safety data at the end of observation period. 4) The remaining subjects dosed within the cohort
Second dose level and higher	1) Two sentinel subjects (1 on SKL24741 and 1 on placebo) 2) 7-day observation period after dosing the first subject with SKL24741 3) The investigator and the Sponsor review all available blinded safety data at the end of observation period. 4) The remaining subjects dosed within the cohort

Dose escalation between the cohorts (dose increase) will only proceed if the safety and tolerability of the previous dose(s) are acceptable as judged by the investigator and the Sponsor. If available/needed, PK analysis results will also be considered. The investigator and the Sponsor may adjust the observation period based on the disposition of SKL24741.

The initiation and the final choice of the dose level for the food and gender effect cohorts (single dose administration) will not be performed until the PK and safety/tolerability are considered to be acceptable for the dose level provided under fasting condition and in healthy male subjects, respectively (Part A, single dose administration) ([Figure 1](#) and [Section 7.1](#)).

The investigator and the Sponsor will take all precautions necessary for studies at an early stage in the development of a new chemical entity. Dose escalation criteria and dose stopping rules ([Section 7.3](#)) will be applicable at any time.

7.3. Dose Escalation Criteria

The investigator and the Sponsor will review all available blinded safety (and applicable PK) data in a blinding fashion at the end of each dose group before deciding to escalate to the next dose level. Dose escalation decision will be jointly made by the investigator and the Sponsor. The dose level may be adjusted from the protocol planned dose, if deemed necessary.

The investigator will stop dose escalation or recommend modification of the dose escalation if in his/her judgment, and in consultation with the Sponsor, such action is medically prudent to protect safety of the subjects.

Study drug administration and dose escalation will be discontinued if, within a cohort, 2 or more subjects (for Part A) or 3 or more subjects (for Part B) experience a laboratory

abnormality or significant clinical event (severe or life-threatening), considered by the investigator to be related or possibly related to the study drug.

The initiation and the final choice of the first dose level of Part B (multiple dose administration) will not be performed until the PK, safety, and tolerability at such corresponding dose level after single dose administration (Part A) are assessed and considered to be acceptable.

Dose escalation in Part A and Part B will be stopped based on the dose stopping rules. The situations where the dose stopping rules apply are outlined in [Table 6](#). If one of the following situations occurs, dose will not be escalated.

Table 6: Dose Stopping Rules (Part A and Part B)

Situation 1	PK futility where the magnitude of plasma exposure (AUC) of SKL24741 increase is disproportionate and not considered meaningful regarding the dose increase.
Situation 2	Safety/tolerability profile does not warrant a higher dose to be investigated.
Situation 3	The plasma exposure of SKL2474 exceeds the dose range justified in the dosing rationale (Section 4.2.2).

8. SELECTION OF STUDY POPULATION

Subjects must meet all inclusion and exclusion criteria.

8.1. Inclusion Criteria

1. Male subjects of 18 to 50 years of age (inclusive) except for the gender effect cohort.
2. Able to read, understand, sign, and date a written informed consent form (ICF) before study participation at screening
3. Agree to use 2 highly effective methods of contraception, including at least one barrier method (Section 10.6.7 for details)
4. Body mass index (BMI) between 18.0 and 30.0 kg/m² (inclusive) at screening
5. Judged to be in good health on the basis of medical history, physical examination, and routine laboratory measurements (i.e., without clinically relevant pathology)
6. Normal electrocardiogram (ECG) (12-lead), arterial blood pressure, and heart rate within the normal range of the study center or considered not clinically significant by the investigator and in agreement with the Sponsor
7. Able to understand and comply with protocol requirements and instructions and likely to complete the study as planned
8. For Part A (gender effect cohort): Female of non-childbearing potential (18 to 50 years of age (inclusive)), who have undergone a sterilization procedure at least 6 months prior to dosing with official documentation (e.g., hysteroscopic sterilization, bilateral tubal ligation or bilateral salpingectomy, hysterectomy, or bilateral oophorectomy), or be postmenopausal with amenorrhea for at least 1 year prior to dosing and follicle-stimulating hormone (FSH) serum levels consistent with postmenopausal status and serum pregnancy test at screening and upon admission with a negative result as per Principal Investigator's judgment

8.2. Exclusion Criteria

1. History of any illness or condition that, in the opinion of the investigator, might confound the results of the study or pose an additional risk in administering study drug to the subjects
2. Smokers (subjects who have smoked within 6 months at screening or those with positive results from smoking screening)
3. Cholecystectomy and/or surgery of the gastrointestinal tract that could interfere with pharmacokinetics of the trial medication (except appendectomy and simple hernia repair).
4. Regular treatment with prescription medications. Subjects should have ended any prescription medications at least 14 days before the first dosing of the study drug. Potential subjects should only stop any prescribed medication at the direction of a physician.

5. Regular treatment with nonprescription medications. Subjects should have ended any nonprescription medications at least 14 days before the first dosing of the study drug. Potential subjects should consult a physician before stopping any regular treatment with nonprescription medication.
6. Consumption of herbal medications, dietary supplements, and specific fruit products. Subjects should have stopped consumption of herbal medications or dietary supplements (e.g., St. John's Wort, ginkgo biloba, and garlic supplements), vitamins, and grapefruit or grapefruit juice, or Seville oranges at least 14 days before the first dosing of study drug.
7. History of drug or alcohol abuse or addiction within 2 years before the start of study drug dosing, or a positive test results for alcohol or drugs of abuse, such as amphetamine, barbiturate, benzodiazepine, cocaine, methadone, opiates, oxycodone, phencyclidine, propoxyphene, cannabinoid (THC), MDMA (Ecstasy), methaqualone, and tricyclic antidepressant (TCA).
8. Regular consumption of more than 2 units of alcoholic beverages per day or more than 14 units per week (1 unit of alcohol equals 1 pint [473 mL] of beer or lager, 1 glass [125 mL] of wine, 25 mL shot of 40% spirit) before screening. Subjects may not consume any alcohol from 72 hours before the first dosing of study drug through the completion of the last PK sampling.
9. Consumption of an average of more than 5 servings (8 ounces per serving) per day of coffee, cola, or other caffeinated beverage before screening. Subjects may not consume any caffeinated beverages from 48 hours prior to dosing until the collection of the last PK sample.
10. Participation in a clinical study involving administration of either an investigational or a marketed drug within 2 months or 7 half-lives (whichever is longer) before screening.
11. Blood donation or a significant loss of blood within 60 days of the start of study drug dosing or donation of more than 1 unit of plasma within 7 days before screening.
12. Positive result at screening for any of the following infectious disease tests: hepatitis B surface antigen (HBsAg), hepatitis C virus antibody (HCV Ab), human immunodeficiency virus antigen and antibody (HIV Ag, HIV Ab)
13. Illness within 5 days before the start of study drug dosing ("illness" is defined as an acute [serious or non-serious] condition [e.g., the flu or the common cold])
14. History of any known relevant allergy/hypersensitivity (including allergy to the trial medication or its excipients)
15. Subject who is judged not eligible for study participation by investigator

8.3. Life Style Guidelines

8.3.1. Meals and Dietary Restrictions

Subjects will not be allowed to eat or drink grapefruit or grapefruit-related citrus fruits (e.g., Seville oranges, and pomelos) from 14 days prior to the first dose (Exclusion criteria (Section 8.2) and [Appendix B](#)) of study medication until the Follow-up visit.

Clinical Chemistry Assessments:

- Clinical laboratory specimens are to be collected under fasting condition. Subjects should not take food or fluids, except of water, for at least 6 hours prior to specimen collection (Section 10.6.2).

Dosing Days:

- Food and fluid intake restrictions associated with study drug administration are described in Section 9.3.
- Meal intake should be avoided within 1 hour of ECG data collection during the extensive triplicate 12-lead ECG.
- Lunch will be provided approximately 4 to 5 hours after dosing.
- Dinner will be provided approximately 9 to 10 hours after dosing.
- An evening snack will be permitted.

8.3.2. Alcohol, Caffeine, and Tobacco

- Alcohol, caffeine, and tobacco restrictions are specified in exclusion criteria (Section 8.2). Subjects may undergo an alcohol test at the discretion of the investigator.

A table of study restrictions is provided in [Appendix B](#).

8.3.3. Activity

Subjects will abstain from strenuous exercise (e.g., heavy lifting, weight training or aerobics) for at least 48 hours prior to each blood collection for clinical laboratory tests. Walking at a normal pace will be permitted.

8.4. Removal of Subjects in the Study

A subject may be discontinued from the study at any time if the subject, investigator, or Sponsor determines that it is not in the best interest of the subject to continue participation. A subject who prematurely discontinues treatment will be asked to return for a Follow-up visit at 14 to 16 days following administration of the last dose of study drug.

Subjects will be discontinued from the study if:

- they develop a medical condition that requires concomitant therapy with a prohibited medication,

- they develop a serious or life-threatening adverse reaction that places them at immediate risk,
- they develop severe nausea or vomiting,
- their female partner becomes pregnant or if the subject/partner is noncompliant with contraception requirements,
- they are noncompliant with study requirements as determined by the investigator,
- they withdraw consent.

In the event that a subject chooses to withdraw from the study, the investigator should make a reasonable effort to ascertain the reason(s) for withdrawal, while fully respecting the subject's rights.

- If the subject withdraws from the study and also withdraws consent for disclosure of future information, no further evaluations should be performed and no additional data should be collected. The Sponsor may retain and continue to use any data collected before such withdrawal of consent.
- If a subject discontinues due to an adverse event or other medical reason, the subject must continue to be followed at regular intervals until the adverse event normalizes or returns to the subject's baseline condition. SK Life Science, Inc. and the investigator will agree to an acceptable follow-up schedule for these subjects.

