7. STUDY DESIGN

7.1. Overview of Study Design

This is a two-part, double-blinded, randomized study of SKL24741. The schematic of study design is shown in [Figure 1](#). [Table 4](#) further outlines the study design.

Part A is a single-dose escalation study in healthy male subjects, except for the gender effect cohort in healthy female subjects. It is expected that a total of 66 subjects (60 male and 6 female subjects) will be enrolled in Part A. Each subject will be given a single oral dose of study drug capsule (SKL24741 or placebo) on one occasion. There will be 6 new subjects at each dose level (4 subjects randomized to SKL24741 and 2 to placebo) during single-dose escalation. Study drug will be administered under fasting condition, except for one cohort utilized for the food effect assessment at one of the dose levels.

To evaluate the magnitude of the food effect on the disposition of SKL24741, a cohort of subjects will receive a second dose of study drug under fed condition (Period 2) at an appropriate dose level based on PK results. After completing Period 1 (fasting) as part of single dose escalation, these subjects will return to the clinical research unit (CRU) for a second confinement to receive a second single dose (same dose level) of study drug under fed condition. A washout period of at least 14 days is planned between fasting and fed cohorts (i.e., between Period 1 and Period 2). As subjects complete the Follow-up visit of Period 1 and then return to the CRU for re-admission (Day -1 of Period 2), the same study procedures will apply again (including Day -1 procedures) in order to initiate Period 2.

To assess the gender effect on the disposition of SKL24741, a set of 6 female subjects of non-childbearing potential will be treated at one dose level under fasting condition.

At each dose level, except for the food and gender effect cohorts, a sentinel dosing strategy will be used as described in Section [7.2](#).

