8.5. Replacement of Subjects

Subjects who withdraw or are withdrawn during one of the study drug administration periods for reasons unrelated to safety may be replaced in order to have 6 subjects completing each dose level in Part A and 8 completing each dose level in Part B. The numbering of replacement subjects is described in Section [9.4.2](#).

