9.11.2. Concomitant Medications

Subjects will not take any prescription, nonprescription, or herbal medications, dietary supplements, or fruit products listed in exclusion criteria (Section [8.2](#)) during the study until completion of the Follow-up visit assessments.

Acetaminophen is an acceptable concomitant medication. A maximum of 1000 mg within 24 hours may be prescribed by the investigator or designee when necessary. Other medication to treat adverse events may be prescribed only after consultation with the SK Life Science, Inc. Medical Monitor unless the medication is necessary to eliminate an apparent immediate hazard to a subject. The investigator will notify the SK Life Science, Inc. Medical Monitor within 24 hours of prescribing medications to treat adverse events, if indicated.

All concomitant medications (including drug name, dose, route, regimen, start/stop dates, and reason for its use) administered for the time period from administration of the dose of the study drug in Part A or the first dose of study drug in Part B through to the Follow-up visit will be documented in the subject's eCRF.

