10.6.7.2. Pregnancy

If the female partner of a subject becomes pregnant, the subject must permanently discontinue study treatment. The investigator must notify the Medical Monitor, SK Life Science, Inc., and IQVIA by completing the Pregnancy Report form, faxing and emailing the form as per the Table of Contact ([Table 13](#) and [Table 14](#)), within 24 hours of the site's knowledge of the partner's pregnancy. The subject's treatment assignment will be unblinded, and if the subject was taking the active drug, the subject's partner will be followed until the end of pregnancy (e.g., delivery, miscarriage) and the infant exposed in-utero will be followed for 1 year after birth, provided consent is obtained. An ICF will be provided to explain these follow-up activities. Pregnancy does not constitute an adverse event.

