12.1.2. Routine Reporting

For the purposes of this study, the period of observation of adverse events for each subject extends from the signing of the informed consent form until their last visit including the follow-up visit or early termination, whichever is longer.

All events reported by the subject, observed by the clinical staff (events, such as abnormal, clinically significant findings from physical examinations, ECG tracings, laboratory assessments, and vital sign measurements), or elicited by general questioning will be recorded in the Institution's source document and reported as an adverse event and captured in the adverse events CRF. If necessary, every effort will be made to obtain an adequate

follow-up of the subjects. Should any subject choose to withdraw early from the study, they will be advised of the safety precautions to be taken.

Early Termination and End of Study (EOS) visit assessments should be performed, including the following: medical history, vital signs, physical exam, safety and clinical laboratory tests, ECG, peak expiratory flow rate (PEFR), Columbia-Suicide Severity Rating Scale (C-SSRS), and adverse event/concomitant monitoring.

Subjects will be questioned on their health status at the beginning of each visit and before their departure from the clinical site. Open-ended questions will be asked.

Classification will be performed by System Organ Class (SOC) and Preferred Term (PT) using the latest version of Medical Dictionary for Regulatory Activities (MedDRA) at the start of the study.

In general, AEs occurring secondary to other events (e.g., clinical sequelae or a cascade of events) should be identified by their primary cause. For example, if severe vomiting is known to result in dehydration, it is sufficient to record only vomiting as SAE or AE in the CRF. However, medically significant AEs occurring secondary to an initiating event that are separated in time should be recorded as independent events on the CRF.

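### Section 8.4 takes subjects out of the study, not only off drug, for tolerability events; in single-dose Part A this withholds almost no drug and leaves later PK and serial ECGs unsecured

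*Protocol*

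**What the plan says.** Section 8.4 introduces its list with "Subjects will be discontinued from the study if". Among the triggers is "they develop severe nausea or vomiting". The others relevant here are a serious or life-threatening reaction that puts the subject at immediate risk, a condition needing a prohibited medication, and partner pregnancy. An earlier paragraph of 8.4 speaks of stopping treatment early, so the protocol has the narrower term but does not use it for the list.

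Section 7.1 says of Part A: "Each subject will be given a single oral dose of study drug capsule (SKL24741 or placebo) on one occasion". The exception is the food-effect cohort, which returns for a second, fed dose in Period 2.

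What is kept after removal:
- Section 8.4: after discontinuation for an adverse event or other medical reason, "the subject must continue to be followed at regular intervals until the adverse event normalizes", on a schedule the sponsor and investigator agree. Those who stop treatment early are also asked to attend a visit 14 to 16 days after the last dose.
- Section 12.1.2: "Early Termination and End of Study (EOS) visit assessments should be performed, including the following: medical history, vital signs, physical exam". The list goes on to laboratory tests, ECG, PEFR and C-SSRS. PK sampling is not in it.
- Table 1 footnote b: discharge on Day 4 follows the 72-hour PK sample. It does not mention discontinued subjects.

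On partner pregnancy, section 10.6.7.2 says: "If the female partner of a subject becomes pregnant, the subject must permanently discontinue study treatment".

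**The concern.** Removing a subject from a single-dose study after the capsule is swallowed spares that subject no further drug, apart from a Period 2 dose. It does put at risk the timed data that were the reason for dosing.

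Those data have uses. Section 4.2.2 caps human exposure at the exposure seen at the rat NOAEL. Situations 1 and 3 of Table 6 refer to plasma exposure. Section 7.3 requires PK at the corresponding Part A dose to be assessed before Part B starts. The protocol also stresses a steep CNS dose response in animals. A subject with a severe tolerability event is the one whose own profile says most about exposure and tolerability, and there are only 4 active subjects per dose level. Section 11.2 requires sufficient PK data for the PK Population, so a truncated profile may drop out of the PK summaries as well.

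Replacement does not repair this. Section 8.5 says "Subjects who withdraw or are withdrawn during one of the study drug administration periods for reasons unrelated to safety may be replaced". Sections 9.4.2 and 11.1 are broader, but under either rule a replacement restores the count and not the affected subject's profile.

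**Working it through.** **Plan's own figures.** The protocol gives no estimate of lost data and no power calculation. Its subject count reproduces: 10 × 6 + 6 + 4 × 8 = 60 + 6 + 32 = 98. Each of the ten Part A escalation levels has 4 active and 2 placebo subjects, so one active subject is 1/4 = 25% of the active data at a level.

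**Schedule (Table 1 footnotes; sections 10.3.1 and 10.3.2).**
- Plasma, post-dose: 0.25, 0.5, 1, 2, 3, 4, 6, 8, 10, 12, 16, 18, 24, 36, 48, 60, 72 h = 17 samples.
- Urine: 0–4, 4–8, 8–12, 12–24, 24–48, 48–72 h = 6 intervals (not in the food and gender cohorts).
- Triplicate ECG, post-dose: 0.5, 1, 2, 3, 4, 6, 8, 12, 24 h = 9 times (not in the food-effect cohort).

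**Unsecured after removal at time T.** Count the times later than T, and the urine intervals that end later than T. The removal times are illustrative; the protocol gives none.

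| Removal | Plasma | Urine | Triplicate ECG |
|---|---|---|---|
| 4 h | 11/17 | 5/6 | 4/9 |
| 12 h | 7/17 | 3/6 | 1/9 |
| 24 h | 4/17 | 2/6 | 0/9 |

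These are upper bounds: they assume that nothing more is collected. Serial vital signs are left out of the table because sections 10.6.3 and 12.1.2 partly cover them.

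**What the plasma loss means for AUC (assumption).** No human PK is given. Take one compartment with first-order absorption, ka from 0.5 to 2 per hour and half-life from 8 to 24 h, with ke = ln 2 / half-life. Then AUC(0–T) is proportional to (1 − e^(−ke·T))/ke − (1 − e^(−ka·T))/ka, and the fraction observed is AUC(0–T)/AUC(0–72).

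- ka 2, half-life 8 h (ke 0.0866), T = 4: (3.381 − 0.500)/(11.519 − 0.500) = 2.881/11.019 = 0.261.
- ka 0.5, half-life 24 h (ke 0.0289), T = 4: (3.778 − 1.729)/(30.297 − 2.000), about 2.048/28.297 = 0.072.

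Over the whole range, the fraction observed is 7–26% at 4 h, 29–63% at 12 h and 54–87% at 24 h. With tmax = ln(ka/ke)/(ka − ke), tmax runs from 1.64 h to 6.05 h, so a removal at 4 h might miss even Cmax.

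**Which triggers matter in Part A.** The prohibited-medication item is narrower than it looks, because section 9.11.2 says "Other medication to treat adverse events may be prescribed only after consultation with" the Medical Monitor, and allows treatment without that step for an immediate hazard. A subject at immediate risk may be unable to give samples whatever 8.4 says. Timed PK ends at 72 h, during confinement, so partner pregnancy matters for it only if it comes to light in those three days. Severe nausea or vomiting is left as the main practical case.

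**The case against.** The strongest reply is that 8.4 does not stop data collection for these triggers. It ends further evaluation in one case only: a subject who withdraws and also withdraws consent for future information. For adverse events it says the opposite, and the agreed schedule could include the PK samples and ECGs. This stands. A reader might infer that 8.4 orders sampling to stop; it does not. The point is that nothing requires sampling to go on. Footnote b does not settle it, because it does not address discontinued subjects.

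A reader might also infer that removed subjects go unmonitored. They do not: beyond the follow-up already listed, extra vital signs and ECGs may be taken (10.6.3, 10.6.4), and confirmed QTc excursions require repeats at least hourly (10.6.4.1).

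Nor does the stopping rule depend on this. Section 7.3 halts Part A dosing when 2 or more subjects in a cohort have qualifying related or possibly related events, and that needs no PK. Section 7.2 brings PK into escalation only if available or needed, and review is of blinded data. Part B needs PK at the dose level assessed, not a full profile from every active subject.

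On partner pregnancy it is tempting to call 8.4 and 10.6.7.2 contradictory. They are not: a subject who leaves the study has also stopped treatment, so both can be followed. The wording differs, and that is all.

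Finally, one removal list for a two-part study is ordinary drafting, and in Part B removal does withhold drug. True, but the list fits Part A poorly, and a narrower term would serve both parts.

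**Conclusion.** The point holds as a low-cost improvement. Section 8.4 mandates leaving the study where stopping drug would do. In Part A that withholds no drug outside food-effect Period 2, and it leaves the rest of the timed plasma and urine PK and the serial triplicate ECGs unsecured.

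The size is an upper bound. For a removal at 4 h it is 11 of 17 plasma samples, 5 of 6 urine intervals and 4 of 9 ECG times, in 1 of 4 active subjects at a dose level; it shrinks with later removal. The counts come from the protocol. The removal times and the AUC fractions rest on assumptions.

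The main loss is PK and exposure-tolerability information. No direction of bias is claimed: vomiting can lower exposure, so such a profile may mislead in either direction unless it is flagged. That is a reason to collect and mark it.

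**What to change.** Amend 8.4 so that the adverse-event, prohibited-medication and partner-pregnancy items stop any remaining study drug (Part B dosing, food-effect Period 2). Add that scheduled PK and safety assessments continue where safe and feasible unless the subject withdraws consent. For partner pregnancy, adopt the treatment-discontinuation wording of 10.6.7.2. No trigger needs to change.

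PK taken after vomiting or a prohibited medication should be flagged. The rule belongs in the Clinical Pharmacology Analysis Plan, which is not at hand, so its absence from the protocol is not a fault.

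The cost is a wording amendment and one flagging rule; the samples and recordings are already scheduled. The downside is that some Part A subjects stay confined to Day 4 after an event, and some of their PK will need careful interpretation.
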